Of particular interest in younger children is the phenomenon of “Atopic March” which is characterized by a typical sequence of progression of clinical signs of atopic disease. In general, the clinical signs of AD and of food allergies predate the development of asthma and allergic rhinitis, suggesting that AD is an “entry point” for subsequent allergic disease ([Spergel 2003](#)). Severity of AD is correlated with development of asthma and allergic rhinitis ([Zheng 2011](#)).

Infants and young children with severe AD have a reported risk rate of around 60% for developing asthma later on in life compared to a risk of around 30% in patients with mild AD ([Ricci 2006](#)).

Atopic dermatitis is caused by a complex interaction of genetics, defects in skin barrier function, environmental exposure, and immunologic responses. Type 2 helper T cell (Th2) mediated immune response is believed to play a central role in the pathogenesis of AD. The skin lesions of AD are characterized by increased expression of proinflammatory Th2 cytokines, such as interleukin (IL)-4 and IL-13, and by skin infiltration of Th2 cells. The elevated IgE responses and eosinophilia observed in the majority of patients with AD reflects an increased expression of the Th2 cytokines IL-4 and IL-13 ([Leung 1999](#)). Type 2 helper T cell-associated cytokines regulate important barrier related functions, such as epidermal cornification and production of antimicrobial proteins. These cytokines inhibit the production of major terminal differentiation proteins, such as loricrin, filaggrin, involucrin, and the antimicrobial proteins human beta defensin 2 and 3, which in turn, is associated with development of AD ([Howell 2007](#), [Guttman Yassky 2011a](#), [Guttman Yassky 2011b](#)).

The Th2 cytokines also act on keratinocytes and induce production of chemokines, including chemokine (C-C motif) ligand 17 (also known as thymus and activation regulated chemokine [TARC]), and chemokine (C-C motif) ligand 26 (also known as eotaxin-3), which are chemo-attractants for Th2 cells and eosinophils; thus, perpetuating the inflammatory response. Since activation of IL-4 and IL-13 signaling precedes the release of proinflammatory mediators, antagonism of these cytokines has the potential to reduce the Th2 response and provide therapeutic benefit.

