Overall, systemic hypersensitivity has been established as an important identified risk with dupilumab. As protein therapeutics, all monoclonal antibodies (mAbs) are potentially immunogenic. Rare serious and systemic hypersensitivity reactions have been observed in the dupilumab program including serum sickness/serum sickness-like reaction in the adult AD and anaphylaxis related to dupilumab in the adult asthma clinical studies. No event of serum sickness/serum sickness-like reaction or anaphylaxis related to dupilumab has been reported in the adolescent AD program.

In study R668-AD-1539, patients will be monitored at the study center for 2 hours post-dose for the first 3 visits at which study drug is administered to facilitate detection and treatment of any immediate hypersensitivity reactions to the study drug.

An important potential risk “Eosinophilia associated with clinical symptoms” has been observed in the asthma clinical trials (few cases of eosinophilic granulomatosis with polyangiitis and eosinophilic pneumonia) but not in AD clinical studies.

Nonclinical repeat-dose toxicity studies and reproductive and developmental toxicity studies have not identified any general or reproductive toxicology or postnatal effects of anti-IL-4 receptor subunit alpha (anti-IL-4R α) surrogate antibodies in cynomolgus monkeys and mice. These nonclinical data, together with the clinical safety profile of dupilumab to date, support the evaluation of dupilumab in pediatric patients.

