19. Presence of any one or more of the following abnormalities in laboratory test results at screening:

- Platelets $\leq 100 \times 10^3/\mu\text{L}$
- Neutrophils $\leq 1.0 \times 10^3/\mu\text{L}$ for patients < 1 year of age; Neutrophils $\leq 1.5 \times 10^3/\mu\text{L}$ for patients 1 year to < 6 years of age
- Eosinophils $> 5000/\mu\text{L}$
- Creatine phosphokinase (CPK) $> 2.5 \times \text{ULN}$
- Serum creatinine $> 1.5 \times \text{ULN}$

NOTE: If an abnormal value is detected at screening, a repeat test should be performed to confirm the abnormality. If the repeat test confirms the abnormality, the patient will be categorized as a screen failure.

20. Presence of skin comorbidities that may interfere with study assessments. This includes, but is not limited to, conditions like scabies, seborrheic dermatitis, cutaneous T cell lymphoma, psoriasis, etc.

21. History of malignancy at any time before the baseline visit.

22. Diagnosed active endoparasitic infections; suspected or high risk of endoparasitic infection, unless clinical and (if necessary) laboratory assessment have ruled out active infection before randomization.

23. Severe concomitant illness(es) that, in the investigator's judgment, would adversely affect the patient's participation in the study. Examples include, but are not limited to patients with short life expectancy, patients with major congenital malformations, patients with cardiovascular conditions (eg, major, clinically significant congenital cardiovascular abnormalities), severe renal conditions, hepato-biliary conditions (eg, Child-Pugh class B or C), active major autoimmune diseases (eg, lupus, inflammatory bowel disease etc.), other severe endocrinological, gastrointestinal, metabolic, pulmonary, neurological or lymphatic diseases. The specific justification for patients excluded under this criterion will be noted in study documents (chart notes, case report forms [CRF], etc).
24. Any other medical or psychological condition including relevant laboratory abnormalities at screening that, in the opinion of the investigator, suggest a new and/or insufficiently understood disease, may present an unreasonable risk to the study patient as a result of his/her participation in this clinical trial, may make patient's participation unreliable, or may interfere with study assessments. The specific justification for patients excluded under this criterion will be noted in study documents (chart notes, CRF, etc).

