5.4.2.2. Reasons for Temporary Discontinuation of Study Drug

Study drug dosing will be temporarily discontinued in the event of:

- Clinically important laboratory abnormalities, such as:
 - ALT or AST $>3\times$ ULN and $\leq 5\times$ ULN
 - Neutrophils $\leq 1.0\times 10^3/\mu\text{L}$, but $>0.5\times 10^3/\mu\text{L}$ for patients <1 year of age; Neutrophils $\leq 1.5\times 10^3/\mu\text{L}$, but $>0.5\times 10^3/\mu\text{L}$ for patients 1 year to <6 years of age
 - Platelet count $\leq 100\times 10^3/\mu\text{L}$ but $>50\times 10^3/\mu\text{L}$
 - Eosinophils $>5000/\mu\text{L}$
 - CPK $>2.5\times$ ULN
 - Serum creatinine $>1.5\times$ ULN
- Other intercurrent illnesses or major surgery
- An infection that requires parenteral treatment or oral treatment for longer than 2 weeks with antibiotic, antifungal, antiviral, antiparasitic, or antiprotozoal agents

After the condition leading to suspension of dosing normalizes sufficiently, study treatment may resume at the discretion of the principal investigator in consultation with the medical monitor. A decision to discontinue study drug and/or to reinstitute study treatment should be discussed with the medical monitor. The investigator may suspend study treatment at any time, even without consultation with the medical monitor, if the urgency of the situation requires immediate action and if this is determined to be in the patient's best interest. However, the medical monitor should be contacted as soon as possible in any case of study drug discontinuation. Resumption of study treatment after temporary discontinuation should always be discussed with the medical monitor.

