## **5.7. Analysis of Safety Data**

The analysis of safety and tolerability will be performed based on the SAF.

The safety analysis will be based on the reported AEs, clinical laboratory evaluations, physical examination, vital signs and 12-lead ECG.

Thresholds for treatment-emergent Potentially Clinically Significant Values (PCSVs) in laboratory variables and vital signs are defined in Appendix 5. A treatment-emergent PCSV is any PCSV which developed or worsened in severity compared to baseline during the treatment and/or follow-up period. The time interval to detect any event or abnormality is between the first injection of study medication and EOS.

In addition, the summary of safety results (including TEAEs, clinical laboratory, vital signs and ECG) will be performed for subjects who were impacted by COVID-19 pandemic and not impacted by COVID-19 pandemic in each study part, respectively if deemed appropriate. The summary will be performed for pre-, during, and post-COVID-19 periods for patients impacted by COVID-19, if deemed appropriate.

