2 - <6 years	WBC	<3.0 GIGA/L or 3,000 /mm  and ≥ 3.0 GIGA/L or 3,000 /mm  at baseline >16.0 GIGA/L or 16,000 /mm  and ≤ 16.0 GIGA/L or 16,000 /mm  at baseline	
6 months- <1 year	Lymphocytes (ALC)	<2.0 GIGA/L or 2,000 /mm  and ≥ 2.0 GIGA/L or 2,000 /mm  at baseline >17.0 GIGA/L or 17,000/mm  and ≤17.0 GIGA/L or 17,000 /mm  at baseline	

≥1 - <6 years	Lymphocytes (ALC)	<1.0 GIGA/L or 1,000 /mm  and ≥ 1.0 GIGA/L or 1,000 /mm  at baseline >10.5 GIGA/L or 10,500/mm  and ≤10.5 GIGA/L or 10,500 /mm  at baseline	
6 months - <6 years	Absolute Neutrophil Count (ANC)	<1.2 GIGA/L or 1,200 /mm  and ≥ 1.2 GIGA/L or 1,200 /mm  at baseline (3-24 months)	
6 months - <6 years	Eosinophils	(>0.5 Giga/L and >ULN) and (≤0.5 Giga/L or ≤ ULN at baseline)	
6 - 23 months	Hemoglobin	< 1.40 mmol/L or 9.0 g/dL and ≥ 1.40 mmol/L or 9.0 g/dL at baseline or any decrease ≥ 0.31 mmol/L or 2 g/dL	
2 - <6 years	Hemoglobin	< 1.55 mmol/L or 10.0 g/dL and ≥ 1.55 mmol/L or 10.0 g/dL at baseline or any decrease ≥ 0.31 mmol/L or 2 g/dL	
6 - 23 months	Hematocrit	< 0.29 l/l or 29 % and ≥ 0.29 l/l or 29 % at baseline > 0.42 l/l or 42 % and ≤0.42 l/l or 42 % at baseline	
2 - <6 years	Hematocrit	< 0.32 l/l or 32 % and ≥ 0.32 l/l or 32 % at baseline > 0.47 l/l or 47 % and ≤ 0.47 l/l or 47 % at baseline	

6 months - <6 years	Platelets	<100 GIGA/L or 100,000 /mm  and ≥ 100 GIGA/L or 100,000 /mm  at baseline > 700 GIGA/L or 700,000 /mm  and ≤700 GIGA/L or 700,000 /mm  at baseline	
	ECG parameters		Ref. : Rijnbeek P.R. et al., Eur Heart J 2001; Davignon A. et al., Ped Cardiol 1979/1980; Semizel E.et al., Cardiol Young 2008; Mulberg AE et al. Pediatric Drug Development Concepts and applications. John Wiley & sons, Inc. 2009
6 - 23 months	PR	≥140 ms and <140 ms at baseline	
2 - <6 years	PR	≥160 ms and <160 ms at baseline	
6 - 23 months	QRS	≥85 ms and <85 ms at baseline	
2 - <6 years	QRS	≥95 ms and <95 ms at baseline	
6 months - <6 years	QTc	Absolute values (ms) Borderline: 431-450 ms and <431 ms at baseline Prolonged*: >450 to <500 ms and ≤450 ms at baseline Additional: ≥500 ms and <500 ms at baseline  Increase from baseline	To be applied to QTcF *QTc prolonged and DQTc>60 ms are the PCSA to be identified in individual subjects/patients listings.

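### The single eosinophil PCSV level can never count a child whose baseline is already above 0.5 Giga/L and the ULN, even if the count later passes 5000/µL

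*SAP*

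**What the plan says.** The hematology part of SAP Appendix 5 has one eosinophil row for all ages from 6 months to under 6 years. Stripped of its outer brackets, it reads ">0.5 Giga/L and >ULN) and (≤0.5 Giga/L or ≤ ULN at baseline". It has no higher level and no change-from-baseline component.

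SAP 5.7 defines the general term more broadly: "A treatment-emergent PCSV is any PCSV which developed or worsened in severity compared to baseline". SAP 5.7.2 plans the laboratory PCSV summary twice, once for all patients in the safety analysis set (SAF) and once for those who did not meet the criterion at baseline.

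The protocol treats eosinophils as a parameter to watch. Section 1.2.3.2 lists eosinophilia among the common adverse reactions in adults with atopic dermatitis (AD). Section 7.2.3 makes symptomatic eosinophilia an adverse event of special interest (AESI). Section 5.4.2.2 temporarily stops dosing above 5000/µL, and exclusion criterion 19 in Section 4.2.2 uses the same figure at screening. Section 1.1 refers in general terms to "The elevated IgE responses and eosinophilia observed in the majority of patients with AD".

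**The concern.** A treatment-emergent PCSV table is meant to show, by arm, how many children developed a laboratory value worth attention. For eosinophils, the only level is one tenth of the protocol's own action level, and it counts only children who start below it. Entry is allowed up to 5.0 Giga/L. A child enrolled with a raised count who then rises past the hold level is therefore left out of the numerator, while a small step across 0.5 Giga/L from a normal baseline can be included.

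At stake is the threshold-based arm comparison for a laboratory parameter that has both a dosing-hold rule and a related AESI. If dupilumab raised counts mainly in children who were already eosinophilic, this table would not show it.

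**Working it through.** The plan states no figure to reproduce, so the check is of the logic of the row.

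**Inputs**
- Criterion: SAP Appendix 5, eosinophil row.
- Hold level: Protocol 5.4.2.2, above 5000/µL. 5000 per µL × 10^6 µL per litre = 5.0 × 10^9/L = 5.0 Giga/L, and 5.0 / 0.5 = 10 times the PCSV cut.
- Highest baseline that can enter: 5.0 Giga/L (Protocol 4.2.2, criterion 19).
- Eosinophil ULN: not in the documents. Assumed at 0.4, 0.5, 0.7, 1.0 and 1.5 Giga/L.

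**Step 1: the rule.** Counted = (post > 0.5 and post > ULN) and (baseline ≤ 0.5 or baseline ≤ ULN). The second bracket fails exactly when baseline > 0.5 and baseline > ULN, that is, when baseline > max(0.5, ULN). No post-baseline value can then satisfy the rule.

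**Step 2: the range that cannot be counted.** The rule was evaluated for baselines from 0 to 5.0 in steps of 0.01, with later values of 5.01, 6, 10 and 20 Giga/L.

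| Assumed ULN | Baselines never counted |
|---|---|
| 0.4 | 0.51 to 5.0 |
| 0.5 | 0.51 to 5.0 |
| 0.7 | 0.71 to 5.0 |
| 1.0 | 1.01 to 5.0 |
| 1.5 | 1.51 to 5.0 |

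Every baseline below these ranges is counted when the later value exceeds 5.0. The loss is therefore confined to children who start above the cut, and it shrinks as the ULN rises.

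**Step 3: examples (ULN assumed 0.5), with the row proposed below alongside.**

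| Baseline → later | Existing row | Added row (> 5.0, baseline ≤ 5.0) |
|---|---|---|
| 0.4 → 0.6 | counted | not counted |
| 0.4 → 6.0 | counted | counted |
| 0.8 → 6.0 (6.0 / 0.8 = 7.5-fold) | not counted | counted |
| 2.0 → 6.0 | not counted | counted |
| 4.9 → 20 | not counted | counted |
| 0.8 → 4.9 (4.9 / 0.8 ≈ 6.1-fold) | not counted | not counted |

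**Step 4: against SAP 5.7.** Worsening in severity needs either a second severity level or a change component. The eosinophil row has neither, so that half of the definition cannot operate. The two populations in SAP 5.7.2 do not help: with a recorded baseline, the all-SAF table and the not-met-at-baseline table have the same numerator and differ only in denominator.

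**Step 5: what else would show such a rise.**
- By-visit descriptive statistics (SAP 5 and 5.7.2) include the third quartile and maximum. A maximum above 5.0 shows that at least one child crossed, not how many. Under SAP 6.4, unscheduled values are mapped to a visit only when the scheduled value is unavailable, whereas PCSV detection uses both.
- Listings flag out-of-range values (Protocol 9.5.3.2) but are not summaries by arm.
- The shift table is optional and normal/abnormal, so a raised count that rises further stays in the same cell.
- The AESI search in SAP Appendix 4 works on coded adverse events. Under Protocol 7.2.5, a dosing change already stipulated by the protocol does not by itself make a laboratory value an adverse event, although symptoms, further diagnostic testing or added treatment can.

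**The case against.** The strongest reply is that this is the convention of the appendix. Most laboratory rows use one level per direction with a not-met-at-baseline condition, nothing requires PCSV levels to match dosing-hold levels, and extreme counts would still appear in maxima, listings and, where reported, adverse event tables. That stands as far as it goes, and it limits the consequence to one table.

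Two things set eosinophils apart. First, entry criteria keep children from starting beyond the PCSV level for some other parameters: platelets at or below 100 × 10^3/µL are excluded and the low PCSV is below 100 Giga/L; CPK above 2.5 times ULN is excluded and the PCSV starts at 3 times. Eosinophils may start at up to 10 times the 0.5 Giga/L cut. Second, the appendix departs from single levels elsewhere: QTc has several absolute and change levels, and hemoglobin has a fall-from-baseline component.

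A reader might infer more than the documents support:
- That most children in this trial cannot be counted. Protocol 1.1 is a background statement about AD patients in general, with no cut-off and no trial data, and the ULN is not given. No number of children can be derived.
- That the eosinophil comparison is worthless. The row still compares arms among children with lower baselines and does count their rises past 5.0 Giga/L.
- That symptomatic eosinophilia is an observed problem in AD. Protocol 1.2.3.2 says it "has been observed in the asthma clinical trials (few cases of eosinophilic granulomatosis with polyangiitis and eosinophilic pneumonia"), but the same sentence adds that it was not seen in AD studies. No document says how often counts pass 5000/µL.

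**Conclusion.** The gap is real but narrow. For any ULN, a child with a baseline above max(0.5 Giga/L, ULN) cannot have a treatment-emergent eosinophil PCSV, and the row cannot deliver the worsening part of SAP 5.7. This follows from the wording alone. How many children it affects depends on the central laboratory's ULN and the baseline distribution, neither of which is in the documents. Across the assumed ULNs, the uncounted range starts between 0.51 and 1.51 Giga/L and runs to 5.0. No efficacy or AESI analysis is affected. What the plan lacks is a specified count and percentage per arm of children who newly pass the level on which the protocol itself acts. That is worth correcting, but it does not undermine the safety plan as a whole.

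**What to change.** Keep the existing eosinophil row in SAP Appendix 5 and add a second: post-baseline above 5.0 Giga/L with baseline at or below 5.0 Giga/L. Tabulate it by arm in the SAF, stating that children with baselines above 0.5 Giga/L and the ULN are included. Hematology is scheduled at screening and next at week 4, so baseline will normally be the screening value, which criterion 19 holds at or below 5000/µL. Nearly every randomised child should therefore be evaluable.

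The cost is one row, its programming and one extra table line, with no new data. It borrows the protocol's existing figure for tabulation only and changes no dosing or other clinical rule. The added row does not fully restore the worsening part of SAP 5.7: a rise such as 0.8 to 4.9 Giga/L would still be uncounted. SAP 5.7 should say so, so that the definition and the appendix agree.

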## APPENDIX 6. RESCUE TREATMENTS

Algorithm for RESCUE TREATMENTS

### 1. Not required to adjudicate rescue treatment:

#### a. Always considered rescue:

Following post-baseline medications (WHODD-coded) given for indications consistent with AD

- ATC2 = CORTICOSTEROIDS FOR SYSTEMIC USE unless used before day 15
- ATC2 = IMMUNOSUPPRESSANTS unless used before day 15
- Preferred Drug Name = Ciclosporin
- Preferred Drug Name = Methotrexate
- Preferred Drug Name = Mycophenolate sodium
- Preferred Drug Name = Mycophenolic acid
- Preferred Drug Name = Mycophenolate mofetil
- Preferred Drug Name = Azathioprine

#### b. Never considered rescue

- ATC2 = EMOLLIENTS AND PROTECTIVES
- ATC2 = VASOPROTECTIVES
- ATC2 = ANALGESICS
- ATC2 = ANTI-ACNE PREPARATIONS
- ATC2 = TOPICAL PRODUCTS FOR JOINT AND MUSCULAR PAIN
- ATC2 = ANTIBIOTICS AND CHEMOTHERAPEUTICS FOR DERMATOLOGICAL USE
- ATC2 = ANTIVIRALS FOR SYSTEMIC USE

- ATC2 = ANTIFUNGALS FOR DERMATOLOGICAL USE
- ATC2 = ANTISEPTICS AND DISINFECTANTS
- ATC2 = ANTIHISTAMINES FOR SYSTEMIC USE
- ATC2 = ANTIPRURITICS, INCL. ANTIHISTAMINES, ANESTHETICS, ETC.
- ATC2 = GENERAL NUTRIENTS
- ATC2 = VITAMINS
- ATC2 = DRUGS FOR OBSTRUCTIVE AIRWAY DISEASES
- ATC2 = OPHTHALMOLOGICALS
- ATC2 = ANTIINFLAMMATORY AND ANTIRHEUMATIC PRODUCTS
- ATC2 = PSYCHOLEPTICS
- ATC4 = CORTICOSTEROIDS, WEAK (GROUP I)
- ATC1 = ANTIINFECTIVES FOR SYSTEMIC USE
- ATC1 = BLOOD AND BLOOD FORMING ORGANS
- ATC1 = ALIMENTARY TRACT AND METABOLISM
- ATC1 = MUSCULO-SKELETAL SYSTEM
- ATC2 = COUGH AND COLD PREPARATIONS
- ATC2 = CORTICOSTEROIDS, DERMATOLOGICAL PREPARATIONS, if  
used before Day 15
- Preferred Drug Name = Tacrolimus, if used before Day 15
- Preferred Drug Name = Pimecrolimus, if used before Day 15
- Preferred Drug Name= Crisaborole, if used before Day 15

A blinded review of all post-baseline medications to adjudicate rescue treatment, based on medical judgement, may be performed in addition. A listing of treatments classified as rescue/non-rescue in a manner inconsistent with the classification under #1 will be provided, along with supporting rationale.

**2. Required to adjudicate rescue treatment:**

- All other medications (not noted in **1** above) given for indications consistent with AD
- Medications noted in **1a** above, when given for indications not consistent with AD

 Below is a list of indications consistent with AD based on PT level from concomitant medication/procedure data using MedDRA dictionary

System Organ Class	High Level Term	Preferred Term	Preferred Term Code
Infections and infestations	Bacterial infections NEC	Eczema impetiginous	10051890
Infections and infestations	Skin structures and soft tissue infections	Dermatitis infected	10012470
Infections and infestations	Skin structures and soft tissue infections	Eczema infected	10014199
Skin and subcutaneous tissue disorders	Dermatitis and eczema	Dermatitis	10012431
Skin and subcutaneous tissue disorders	Dermatitis and eczema	Dermatitis atopic	10012438
Skin and subcutaneous tissue disorders	Dermatitis and eczema	Eczema	10014184
Skin and subcutaneous tissue disorders	Dermatitis and eczema	Neurodermatitis	10029263

Signature Page for VV-RIM-00152867 v1.0

ESig Approval	 000
---------------	---

ESig Approval	 000
---------------	---

ESig Approval	 -2021 13:21:38 GMT+0000
---------------	---

Signature Page for VV-RIM-00152867 v1.0 Approved
